5. Safety Evaluations 13

5.1. Adverse Events 13

5.2. Serious Adverse Events 13

5.3. Complaint Handling 14

6. Patient Consent to Release Information, Ethical Review, and
Regulatory Considerations 15

6.1. Patient Consent to Release Information 15

6.2. Ethical Review and Regulatory Considerations 15

7. Record Keeping, Data Reporting, Data Quality Assurance, and
Publications 16

8. References 17

Table of Contents (concluded)

List of Observational Study Description Attachments

Attachment	Page
Attachment 1. Observational Study Description Attachment B034.1. Data Collection Schedule.....	18
Attachment 2. Protocol Amendment F1D-MC-B034(c) Post-Injection Syndrome in Patients with Schizophrenia Receiving Olanzapine Long-Acting Injection.....	21

Post-Injection Syndrome in Patients with Schizophrenia Receiving Olanzapine Long-Acting Injection Summary of the Study

Study F1D-MC-B034 (B034) is a noninterventional prospective study designed to assess the incidence of Post-Injection Syndrome events in patients treated with olanzapine Long-Acting Injection (olanzapine LAI). This study is planned to be conducted in multiple countries where olanzapine LAI is marketed. For Study B034, a Post-Injection Syndrome event is defined as an event reported in temporal association with an injection of olanzapine LAI that presents with signs and symptoms consistent with olanzapine overdose (post injection). Most patients have developed symptoms of sedation (ranging from mild in severity up to coma) and/or delirium (including confusion, disorientation, agitation, anxiety, and other cognitive impairment). Other symptoms noted include extrapyramidal symptoms, dysarthria, ataxia, aggression, dizziness, weakness, hypertension, or possible convulsion.

The investigator will record on the data capture form all adverse events (AEs) that occur within 24 hours following an injection and will provide a clinical opinion as to whether the patient has experienced a potential Post-Injection Syndrome event. An Adjudication Committee will review all these cases and will determine whether a case of interest is excluded from further categorization.

The study will characterize the clinical presentation and outcomes of Post-Injection Syndrome events, as well as seek to identify potential risk factors associated with their occurrence.

Approximately 5000 patients will enter this multicenter study to achieve 92,500 injections that will be included in event incidence calculations.

1. Introduction

Olanzapine Long-Acting Injection (olanzapine LAI) is a sustained-release intramuscular (IM) dosage formulation of olanzapine, and has been studied in clinical trials since 2000. As of 31 January 2009, over 59,482 injections have been administered to 2,054 patients. As of this cutoff date, 39 Post-Injection syndrome (also known as Post Injection Delirium Sedation Syndrome [PDSS]) events have been reported in 38 patients. Clinical presentation was consistent with many symptoms of oral olanzapine overdose; most patients experiencing a Post-Injection Syndrome event have developed symptoms of sedation (ranging from mild in severity up to coma) and/or delirium (including confusion, disorientation, agitation, anxiety, and other cognitive impairment). Other symptoms seen include extrapyramidal symptoms, dysarthria, ataxia, aggression, dizziness, weakness, hypertension, or possible convulsion. No respiratory depression or clinically significant decreases in blood pressure were noted. Further information on the presentation of these events as well as the possible mechanism for the events can be referenced in publications by Detke et al (2010) and McDonnell et al (2010).

The mechanism of these events is probably related to higher solubility of olanzapine LAI in blood than in muscle. Increased contact with a substantial volume of blood could occur in several ways: partial injection into the vasculature, vessel injury associated with the IM injection, such as a nick or puncture of the blood vessel, or substantial bleeding at the injection site. With any of these, there could be a “rapid release” of a portion of the olanzapine LAI dose. Higher than expected systemic olanzapine concentrations have been observed in patients experiencing a Post-Injection Syndrome event.

As of 31 January 2009, the incidence of Post-Injection syndrome events in patients treated with olanzapine LAI in clinical trials is approximately 0.07% of injections (1.85% of patients). In most cases, initial signs and symptoms related to this event have appeared within 1 hour following injection, and in all cases full recovery was reported to have occurred within 24 to 72 hours after injection. Events occurred rarely (<1 in 1000 injections) between 1 and 3 hours, and very rarely (<1 in 10,000 injections) after 3 hours.

This observational trial is designed to estimate the incidence of Post-Injection Syndrome events in “real world” clinical practice, as well as better characterize the clinical presentation and outcomes. This study will also seek to identify potential risk factors associated with Post-Injection Syndrome events.

2. Objectives

2.1. Primary Objective

The primary objective of this study is to:

- estimate the incidence per injection and per patient of Post-Injection Syndrome events in schizophrenia patients receiving olanzapine LAI.

2.2. Secondary Objectives

The secondary objectives of this study are to:

- further characterize the clinical presentation, including the outcomes of Post-Injection Syndrome events
- identify potential risk factors associated with Post-Injection Syndrome events
- characterize hospitalization at baseline (previous 6- or 12-month) and postbaseline

3. Methods

3.1. Summary of Study Design

Study F1D-MC-B034 is a prospective observational study to assess the incidence of Post-Injection Syndrome events in schizophrenia patients receiving olanzapine LAI.

Observational studies represent noninterventional research; therefore, these studies do not involve randomization of patients to particular comparator arms or therapies. The term “noninterventional” means that the healthcare provider’s decisions regarding the proper treatment and care of the patient are made in the course of normal clinical practice. Patients enrolled in this study are enrolling for the collection of their data on observations made during normal clinical practice.

The study is planned to be conducted at sites in multiple countries where olanzapine LAI is marketed. Patient treatment, dosing, and AE management are at the discretion of the investigator. For this study, based upon the investigator’s clinical judgment, a Post-Injection Syndrome event is defined as an event or events reported in temporal association with an injection of olanzapine LAI that presents with signs and symptoms consistent with olanzapine overdose. An Adjudication Committee will review all serious adverse events in this study to determine whether a case of interest is a confirmed Post-Injection Syndrome event based upon the committee’s predefined decision algorithm (see Section 3.3.3).

Approximately 5000 patients will enter this study, to achieve an estimated number of 92,500 injections. Additional patients may be needed to achieve the desired number of injections.

Study enrollment will occur when the patient provides consent to release medical information. Data collection point (DCP) 1 then occurs at the first olanzapine LAI injection after the patient provides consent. At DCP 1, the investigator will record baseline information. Patients do not need to be olanzapine LAI naive to participate in this study. The frequency of DCPs will depend on the frequency that the patient is receiving olanzapine LAI injections. Data collected at every DCP (i.e., every injection of olanzapine LAI) are summarized in Attachment B034.1.

More detailed data will be recorded if the patient has a potential Post-Injection Syndrome event, if applicable and if possible.

3.2. Study Population

Eligible patients will include adult patients with schizophrenia whose physician has decided to treat with olanzapine LAI.

3.2.1. Selection Criteria

Patients are eligible to be included in the study if they meet all of the following criteria:

- They are male or female patients, at least 18 years of age who have been diagnosed with schizophrenia.

- They are willing to participate in the study and have signed a consent form to release medical information.
- They do **not** meet **any** of the following criteria:
 - They are investigator site personnel directly affiliated with the study and/or their immediate family. Immediate family is defined as a spouse, parent, child, or sibling, whether biological or legally adopted.
 - They are Lilly employees.
 - They are unwilling to provide written consent to release medical information or other required forms to participate in the study.

3.2.2. Patient Groups

There are no assigned treatment groups for this study.

3.2.3. Patient Discontinuation from Study

Possible reasons for discontinuation of a patient from observation include death, AE, patient decision, investigator decision, lost to follow-up, and sponsor decision. All information related to a death (regardless of relationship to the study or study medication) will be collected.

3.3. Study Therapies

All patients will receive commercially-available olanzapine LAI in accordance with their physician's standard of care.

Treatment is solely at the discretion of the physician and the patient. Treatment for schizophrenia will be prescribed in the usual standard of care and will not be provided by the study sponsor. Participation in the study will in no way influence payment or reimbursement for any treatment received by patients during the study.

It is recommended that investigators follow the country- or region-specific labeling (e.g., Summary of Product Characteristics).

3.3.1. Assessment of Treatment Outcomes

Study enrollment will occur when the patient provides consent to release medical information. DCP 1 will occur at the first administration of olanzapine LAI after consent. The investigator will record all baseline information, including demographics, year of initial diagnosis of schizophrenia, all prior depot antipsychotic medication use, history of psychiatric drug use, and previous psychiatric hospitalization information.

The frequency of DCPs will depend on the frequency that the patient is receiving olanzapine LAI. Every administration of olanzapine LAI will be considered a DCP. If the patient is seen by study staff, but does not receive olanzapine LAI, this is not to be reported as a new DCP in the electronic data capture system. Any relevant observations made by the investigator or reported to the investigator are to be recorded on the appropriate data form (electronic case report form).

Data collected at every DCP will include all AEs, all current medications (including over-the-counter), recreational substance use in the past 24 hours (except for nicotine and caffeine use), mental status at the end of the observation period, date and time of injection, size of needle (length and gauge) used for injection, clinical setting of injection administration, dose, collection of the frequency of metabolic monitoring, and psychiatric hospitalization information. The frequency of metabolic monitoring is being collected to assess adherence to label or metabolic guideline recommendations. The actual lab results (if performed) will not be collected. These data collected at every DCP are summarized in Attachment B034.1.

More detailed data are to be recorded if the patient has a potential post-injection syndrome event, if applicable and if possible, such as date/time of event onset and date of event resolution

Attachment B034.1 outlines the data to be collected at each DCP.

3.3.2. Operational Definition of Post-Injection Syndrome Event

A patient should be considered by the investigator to have a potential Post-Injection Syndrome event if, after ruling out oral overdose of any drug, based upon the investigator's clinical judgment, the following two conditions are met:

- The patient presents with signs and symptoms (most commonly sedation and delirium-related AEs) of clinical severity consistent with those reported with an olanzapine overdose, and
- The signs and symptoms are reported in temporal association with an injection of olanzapine LAI.

Most patients who experienced a Post-Injection Syndrome event have developed symptoms of sedation (ranging from mild in severity up to coma) and/or delirium (including confusion, disorientation, agitation, anxiety, and other cognitive impairment). Other symptoms noted include extrapyramidal symptoms, dysarthria, ataxia, aggression, dizziness, weakness, hypertension, or possible convulsion.

Detailed training regarding the signs and symptoms of olanzapine overdose will be provided to the study team and study site staff.

3.3.3. Adjudication Committee Review of Post-Injection Syndrome Events

An Adjudication Committee will review all serious adverse events including cases reported as potential Post-Injection Syndrome events by the study investigator. To provide consistency and to minimize the occurrence of false positive assessments, the committee will utilize predefined criteria when reviewing potential Post-Injection Syndrome events. The determination of whether the reported events meet the predefined Post-Injection Syndrome events criteria will be decided by consensus of the Adjudication Committee. All members of the Adjudication Committee will have experience in assessing and identifying Post-Injection syndrome events. The Adjudication Committee will not include a B034 study investigator as a member.

4. Sample Size and Statistical Methods

4.1. Determination of Sample Size

Based on the patient retention rates of Study HGKB through 30 September 2007, it is anticipated that the approximately 5000 patients to be observed in Study B034 will experience at least 92,500 injections. Based on the estimated incidence by injection (0.072%) as of 15 July 2008, this number of injections will have at least 80% power to show the proportion of injections resulting in a Post-Injection Syndrome event (θ) is less than 0.10%. It is the intent of this study to show the rate of Post-Injection Syndrome events in olanzapine LAI to be less than 0.10%. More patients may need to be enrolled to ensure that at least 92,500 injections are administered.

Assuming a null hypothesis proportion θ_0 to be 0.072%, an exact binomial test with a nominal 0.05 two-sided significance level will have at least 80% power to detect the difference between θ_0 of 0.072% and the alternative proportion of 0.10% when the number of injections is 92,500. In terms of events per patient, assuming a null hypothesis θ_0 to be 1.36% (estimated incidence by patient as of 15 July 2008), this sample size will allow for at least 70% power to detect the difference between θ_0 and the alternative proportion of 2% at the 0.05 two-sided significance level.

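### The per-patient power in Section 4.1 (at least 70%) is not the power of the test described there, which is about 94% with 5000 patients

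*Protocol*

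**What the plan says.** The primary objective (Protocol, Section 2.1) is to estimate incidence both per injection and per patient. Section 4.1 gives a power statement for each.

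- **Size.** "it is anticipated that the approximately 5000 patients to be observed in Study B034 will experience at least 92,500 injections".
- **Per injection.** "an exact binomial test with a nominal 0.05 two-sided significance level will have at least 80% power" for "the difference between θ_0 of 0.072% and the alternative proportion of 0.10% when the number of injections is 92,500".
- **Per patient.** The null is 1.36%, the estimate as of 15 July 2008. The text says "this sample size will allow for at least 70% power to detect the difference between θ_0 and the alternative proportion of 2" (that is, 2%), again at a two-sided 0.05 level.

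Section 3.2.2 states that there are no assigned treatment groups. Both statements in Section 4.1 compare one observed proportion with a fixed θ_0. The Introduction gives later figures, as of 31 January 2009: 39 events in 38 of 2,054 patients after more than 59,482 injections, or about 0.07% of injections and 1.85% of patients.

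**The concern.** The two power statements stand side by side, share a level and appear to share a test. The per-injection figure can be reproduced from its inputs. The per-patient figure cannot: 5000 patients are far more than a one-sample test of 1.36% against 2% needs for 70% power.

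A reader of Section 4.1 would conclude that the per-patient half of the primary objective is the weaker half. Under the protocol's own planning values it is the stronger one. A power figure that does not follow from its stated inputs also raises the question of which design it was computed for.

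**Working it through.** **Inputs.** n = 5000 patients, θ_0 = 1.36%, alternative 2%, two-sided 0.05 (Section 4.1). The exact binomial test is named there only for injections, and I assume that it carries over to patients. I use 0.025 in each tail.

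**1. Method check on the per-injection figure (n = 92,500).**
- Null 0.072% (66.6 events expected): reject at 84 or more, since P(X ≥ 84) = 0.0221 and P(X ≥ 83) = 0.0288. Power at 0.10% is 82.5%.
- Reversed, null 0.10% (92.5 expected): reject at 73 or fewer, P(X ≤ 73) = 0.0210. Power at 0.072% is 80.3%.

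Both agree with the printed at least 80%, and the bound is close.

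**2. Per-patient figure, same test (n = 5000).**
- Null 1.36% (5000 × 0.0136 = 68 expected): reject at 85 or more, since P(X ≥ 85) = 0.02496 and P(X ≥ 84) = 0.0324. Power at 2% is P(X ≥ 85) = **94.4%**.
- Reversed, null 2% (100 expected): reject at 80 or fewer, since P(X ≤ 80) = 0.0216 and P(X ≤ 81) = 0.0279. Power at 1.36% is P(X ≤ 80) = **93.4%**.

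**3. Does the choice of one-sample method matter?** The normal approximation is

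Φ[(|p1 − p0|√n − 1.96√(p0(1 − p0))) / √(p1(1 − p1))]

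= Φ[(0.0064 × 70.71 − 1.96 × 0.1158) / 0.1400] = Φ(1.61) = 94.6%.

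With continuity correction it is 94.1%, by arcsine 94.3%, and by the exact test at one-sided 0.05 it is 96.5%. No one-sample variant tried at 5000 patients comes near 70%. For 70% the exact test needs only about 2,470 to 2,620 patients (about 2,610 to 2,840 reversed). These are ranges because exact power is saw-toothed in n.

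**4. Where does 70% appear?** In a two-sample comparison with 5000 patients in each group and p̄ = 1.68%:

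Φ[(|p1 − p0|√n − 1.96√(2p̄(1 − p̄))) / √(p0(1 − p0) + p1(1 − p1))]

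= Φ[(0.4525 − 1.96 × 0.1818) / 0.1817] = Φ(0.53) = **70.2%**.

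That formula treats 1.36% as the estimate from a second group of 5000, not as a fixed value. The same formula with 92,500 injections per group gives 53.8%, so it does not underlie the per-injection figure.

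**5. Exposure behind the per-patient rates.**
- Planned: 92,500 / 5000 = 18.5 injections per patient.
- Behind the Introduction's 1.85%: 59,482 / 2,054 = 29.0 injections per patient.

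Assume a constant, independent risk q per injection, so that the per-patient risk after k injections is 1 − (1 − q)^k.

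| q | k = 18.5 | k = 29.0 |
|---|---|---|
| 39/59,482 = 0.0656% | 1.21% | 1.88% |
| 0.072% | 1.32% | 2.06% |

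The later per-injection rate at 29 injections gives 1.88%, close to the observed 38/2,054 = 1.85%. At the planned 18.5 injections either rate gives a value just below 1.36%.

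**The case against.** The best defence is that the sentence is true. It says at least 70%, and 94% is at least 70%. The error is on the safe side, since the study has more per-patient power than it claims. Little hangs on it: enrolment is driven by the 92,500 injections, the stated intent to show a rate below 0.10% is per injection, and Section 4.2.2.1 plans crude incidences with 95% confidence intervals and no per-patient test against 2%. All of this stands, and it makes the point minor. It does not make the figure right. A lower bound 24 points below the true value, next to one that is tight to within 3 points, misinforms the reader about the design.

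A stronger reading is tempting. The Introduction's 1.85% is more recent than 1.36% and lies close to 2%. Put in its place at n = 5000, it gives power of only about 10% (10.5% as written, 10.2% reversed), and a reader might infer that the claim of at least 70% is false. The documents do not support this. The 1.85% was accrued over about 29 injections per patient, and this study plans 18.5. At that exposure the protocol's per-injection rates imply about 1.2% to 1.3% of patients, where power against 2% is about 96% to 99%. The later per-injection rate is also no higher than the planning rate. Both per-patient figures carry their cut-off dates, so the two sections do not contradict each other. What remains is a reminder that a per-patient incidence has no fixed meaning until the number of injections is stated.

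**Conclusion.** The concern holds as a minor misstatement. For 1.36% against 2% with about 5000 patients, power is about 94% as written and about 93% when 2% is the null. The printed 70% is not the power of this single-group comparison. It coincides with a two-group formula with 5000 per group, but the protocol does not show how it was obtained, so that origin is plausible and not established. The study is not underpowered on this account, and no planned estimate or interval is affected.

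The result assumes that the exact binomial test applies to patients as it does to injections (other one-sample methods change little) and that about 5000 patients contribute. Reading 2% as a bound to be excluded assumes that the aim stated for injections carries over to patients. The exposure argument assumes a constant, independent risk per injection.

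**What to change.** Replace the per-patient sentence in Section 4.1 with text such as: *With about 5000 patients averaging 18.5 injections each, power to show that per-patient incidence is below 2% is about 93% if the true value is 1.36% (exact binomial test, two-sided 0.05).* State that 1.36% and 2% both refer to that exposure, after confirming that this is what was meant. The ratio 1.36/0.072 = 18.9 injections per patient suggests that it is.

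If the 1.85% is mentioned in this context, give its exposure of about 29 injections per patient with it.

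The cost is one or two sentences. Enrolment, data collection and analysis do not change.

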4.2. Statistical and Analytical Plans

4.2.1. General Considerations

Statistical analyses will be performed by the sponsor or their designee. The statistical analysis plan created for this study will contain additional details on planned analyses.

4.2.1.1. Study Population

All patients who provide consent to release information and who fulfill the study entry criteria will be included in the analyses. For those patients who are lost to follow-up, or who drop out of the study, the analyses will include all data up to the point of their last data collection. Due to the observational nature of this study, patients who violate the protocol will be included in the analyses.

4.2.1.2. Missing Data

The statistical analysis plan created for this study will address the handling of missing data.

4.2.1.3. Significance Levels

A confidence interval will be two-sided at a 95% level.

4.2.1.4. Adjustments for Covariates

Due to the observational nature of this study, covariate adjustments will be made to control for biases and confounding where appropriate.

4.2.2. Treatment Outcome Analyses

4.2.2.1. Primary Outcome Analysis

Crude incidence of Post-Injection Syndrome events and 95% confidence intervals will be calculated based on the total number of patients enrolled in the study and the total number of injections given in the study period. Post-Injection Syndrome events used in the incidence calculation will be based on adjudicated cases.

